## Research Design and Methodology

### Design overview

We have planned a randomized pilot study to evaluate the use of two skin-surface electrical stimulation approaches for improving sexual arousal. Subjects will be assigned one of two stimulation approaches and will receive the experimental treatment during a twelve-week test period. Standard sexual function and quality of life surveys will be completed at key time points to evaluate the effects of the experimental stimulation as compared to before study initiation and to look for any long-term residual effect. Participants will also be given a demographics questionnaire once during the study, so that we can evaluate possible stratification among participants and stimulation responders.

### Description of methods and analysis

Patients will be randomly assigned to one of two study groups: receiving DGNS or PTNS. In this pilot study, as has been standard for prior pilot evaluations of DGNS and PTNS [1-5], we will not have a control stimulation paradigm that does not activate the nerves of interest. While this control stimulation is desired for an ultimate demonstration of this approach, its design will be outside the scope of what is feasible with these pilot funds. To date there has only been a single controlled evaluation of PTNS which also included a control stimulation paradigm [6]. We plan to emulate that approach after demonstrating feasibility here. See Figure 1 for the study paradigm.

For subjects assigned to the dorsal genital nerve stimulation test group, electrodes will be placed as in Figure 2. Electrodes will be standard TENS skin-surface electrodes that are 2 cm in diameter. Test electrodes will be placed on either lateral side of the clitoris, with not more than 5 mm to each electrode edge, with cathode indifferent. At the first stimulation session, the pudenda-anal threshold ( $PA_T$ ) for driving reflex closure of the anal sphincter will be determined by starting with a 5 mA, 1 Hz stimuli through the test electrodes and increasing in 5 mA steps until sphincter closure is observed. Thereafter, test stimulation will be applied at 20 Hz and  $2 \times PA_T$  or below a level at which the subject notes discomfort, whichever is lower. The anticipated test amplitude is within 30 – 60 mA [7-9]. After placement of electrodes and draping of the region, stimulation will be applied for 30 minutes in each session.

For subjects assigned to the posterior tibial nerve stimulation test group, the same electrodes as for DGNS will be placed as in Figure 3. The test electrodes will be placed just above the medial malleolus (cathode) and the ipsilateral calcaneus (anode). At the first stimulation session, the test electrode stimulation level will be determined with 1 Hz stimulation at 5 mA and increased in 5 mA levels until a rhythmic flexion of the toes is observed or the patient notes discomfort. Thereafter the test stimulation will be a level just below that at which the motor or discomfort responses occurred [2]. After placement of electrodes and draping of the region, the appropriate stimulation will be applied for 30 minutes in each session. [name] will place the electrodes on subjects at each appointment.

Stimulation effects on sexual arousal are unlikely to be observed in the clinic. If this study is successful, future proposals to investigate underlying mechanisms may evaluate in vivo effects with animal models. We will have subjects complete four standard surveys as has been done for other

[figure not shown]

Figure 1. Study paradigm. Subjects will be randomized into one of two test groups (DGNS/PTNS). Sexual Function and Quality of Life surveys will be taken at study initiation and at 6-week intervals afterwards. The final 6-week period of no stimulation will look for long-term carry over.

neuromodulation studies [1], [6], [10-12]. The Female Sexual Function Index (FSFI) is a standardized survey with 19 questions on sexual health that provides a maximum score of 36 [13] (See Appendix 1 for survey). The short form 36-question (SF-36) quality of life survey was designed for general use in clinical practice [14] and will be used here to assess overall impact (See Appendix 2 for survey). The Measure of Symptoms - American Urological Association Symptom Index is a standardized 8-question survey assessing urologic concerns. The Patients' Global Impression of Change (PGIC) Scale is a 1-question survey designed to assess patients' feelings of improvement after intervention. Subjects will take the four surveys before study initiation (baseline), after each of concurrent 6-week stimulation sessions in the clinic (6weeks; 12weeks), and six weeks after study completion (long-term).

Due to the relatively small sample sizes planned for this study, we will use non-parametric statistical testing. We will use a two-sided Wilcoxon rank sum test to make comparisons of the survey scores among the different subject groups [1], [6], [8], [15], with a significance level of 0.05. FSFI and SF-36 scores will be compared for each of the potential comparisons among the baseline, 6-week and 12-week study time points and at long-term time point, for DGNS and PTNS groups separately.

We plan for a total study size of 30 subjects. 15 subjects will be assigned to each stimulation group – DGNS and PTNS. As this is a pilot study that has not been performed before, we do not have an effect size from which to calculate a target sample size. This study size of 15 subjects for each stimulation approach was selected for two reasons. Our primary factor was that prior pilot studies using these stimulation approaches for other patient groups used similar study sizes of 9-10 subjects [3-4], [8-9]. Our secondary factor was that given the one-year time frame of our planned study, larger sample sizes may not be feasible. If one or both stimulation approaches are successful, larger sample sizes will be performed in subsequent studies.

[figure not shown]

Figure 2. DGNS electrode locations. For experimental DGNS, the TENS unit will be connected to electrodes placed on either side of the clitoris.

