### Collection, analysis and interpretation of results

Each study subject will be assigned an identification number. Only this number will be used to identify subjects in any individual tabulation. It is expected that only group data will be published. If individual subject data is to be published, no identifying information will be included. The study files will be maintained in a secure location. Access to computerized data will be restricted to IRB-approved study personnel. Password authorization will be enforced.

The study coordinator or other research team staff will provide both the FSFI and the SF-36 surveys to each subject, in paper form, upon their initiation into the study. Subjects will be given up to an hour to complete the survey by circling their responses on the paper form. The form for each subject will have the identification number as the only identifying piece of information on it. This same sequence will be performed at the other data collection points – after 6 weeks of testing (in the clinic before the 7th stimulation session) and after the 12th session. For the 6-week post-trial follow-up, a research staff will contact each subject to complete the survey over the phone, or will allow the subject to complete the survey and mail back in if they will not be visiting the clinic during that time.

As described in the appendices, each survey has a scoring method that yields a total quality of life score and a total sexual satisfaction score. These scores will be compared across the different time points as discussed above. The study team will meet with a statistical consultant (UM Center for Statistical Consulting and Research) to confirm correct approaches and conclusions. The study team will also compare the results found to other reported studies in the literature that used similar methods and analysis approaches for consistency. As described in the appendices, each survey has sub-sections that we may compare individually, if the data suggests any sub-section trends.

Data collection will be limited to the investigators and the research staff. All study personnel who have access to the data will be educated regarding the need to protect confidentiality and the procedure to be followed to ensure such protection. All staff will also be required to sign a standard medical record confidentiality agreement.

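### The only named test is the unpaired Wilcoxon rank sum, but the listed comparisons are between repeat scores of the same women, and no paired method is named

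*Combined protocol and SAP*

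**What the plan says.** All of this is in the Combined protocol and SAP.

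- **Arms.** Description of methods and analysis: "Patients will be randomly assigned to one of two study groups: receiving DGNS or PTNS".
- **Test.** The statistical paragraph of that section says "We will use a two-sided Wilcoxon rank sum test to make comparisons of the survey scores among the different subject groups", "with a significance level of 0.05".
- **Comparisons.** The next sentence lists them: "FSFI and SF-36 scores will be compared for each of the potential comparisons among the baseline, 6-week and 12-week study time points", and then "at long-term time point, for DGNS and PTNS groups separately".
- **Purpose.** Design overview says the surveys serve "to evaluate the effects of the experimental stimulation as compared to before study initiation and to look for any long-term residual effect".
- **Later restatement.** Collection, analysis and interpretation of results adds no test: "These scores will be compared across the different time points as discussed above". It also plans a meeting with a statistical consultant to check the approach.
- **Record linkage.** The same section says "The form for each subject will have the identification number as the only identifying piece of information on it".

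The documents name no signed-rank test, change-score analysis, Friedman test, mixed model or other repeated-measures method.

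**The concern.** The rank sum (Mann-Whitney) test assumes two independent samples. Comparing time points separately within DGNS and within PTNS sets each woman's later score against her own earlier one. The text allows two readings:

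1. The rank sum test is used for these within-arm comparisons. That is the wrong test for paired scores.
2. The rank sum test is meant only for DGNS versus PTNS, where it is valid. The time-point comparisons then have no named test.

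The study has no control stimulation, so change from before treatment is the main evidence it can produce. On the first reading, stable differences between women are counted as noise and a real change can be missed. On the second, the within-arm test could be chosen after the scores are seen.

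**Working it through.** **Plan's own figure.** The planned size is 30 women, 15 per arm. It rests on earlier pilot sizes and feasibility, with no effect size or power behind it, so there is no power figure to reproduce. The only stated error rate is 0.05, two-sided.

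**Number of comparisons affected.** If the long-term point is compared with every other point, four time points give C(4,2) = 6 pairs, and 6 × 2 surveys × 2 arms = 24. Counting only pairs among baseline, 6 weeks and 12 weeks, C(3,2) = 3 and 3 × 2 × 2 = 12. The sentence does not settle how the long-term point enters.

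**Why the rank sum is miscalibrated on paired scores.** For two scores with common SD σ and correlation r, the difference in means over n women has variance 2σ²(1 − r)/n. An unpaired test assumes 2σ²/n. In a normal approximation the effective cut-off is 1.96/√(1 − r). At r = 0.5 this is 1.96/0.707 = 2.77, a two-sided tail of about 0.6% instead of 5%.

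**Simulation (first reading only).** n = 15 women measured twice; bivariate normal scores with equal SDs, no ties, no dropout; 40,000 draws per r. Exact critical values were used: rank sum U ≤ 64 (exact size 4.53%), signed-rank W ≤ 25 (exact size 4.79%). The documents give neither r nor an effect size, so both are assumed and shown over a range. Power is rank sum vs signed-rank.

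| r | True size, rank sum | Power, 0.5 SD | Power, 0.7 SD | Power, 1.0 SD |
|---|---|---|---|---|
| 0 | 4.6% | 24% vs 23% | not shown | not shown |
| 0.3 | 2.0% | 20% vs 32% | 41% vs 54% | 74% vs 84% |
| 0.5 | 0.8% | 18% vs 42% | 40% vs 69% | 78% vs 94% |
| 0.7 | 0.15% | 14% vs 62% | 40% vs 89% | 83% vs 99% |
| 0.8 | 0.04% | 12% vs 79% | 40% vs 97% | 86% vs nearly 100% |

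The signed-rank size stays at 4.7% to 5.0% throughout. For r from 0.3 to 0.8 the loss runs from 84 − 74 = 10 points (r = 0.3, 1.0 SD) to 79 − 12 = 67 points (r = 0.8, 0.5 SD).

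A separate run of 20,000 data sets per scenario agrees to within about one percentage point where the two overlap. At a 0.8 SD shift it gives 52% vs 66%, 54% vs 80%, 56% vs 95% and 58% vs 99% for r = 0.3, 0.5, 0.7 and 0.8.

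**Equivalent sample size.** To match the signed-rank test on 15 women, the rank sum on the same kind of paired data needs about 22, 30 and 40 women per arm at 0.5 SD (r = 0.3, 0.5, 0.7), and about 18, 22 and 27 at 1.0 SD. These figures use the normal approximation with continuity correction and 20,000 draws per n.

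**The case against.** The best defence is that the sentence naming the test speaks of subject groups, and the same section uses similar words for the two arms. If the rank sum is meant only between arms, it is valid and the power table does not apply. What remains is an unnamed within-arm test, limited by the general commitment to non-parametric methods and open to correction by the consultant. That reading is reasonable. It does not rescue the plan: the only comparisons actually listed would then have no test, and a later consultation does not pre-specify one.

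Four further points stand as limits on size:

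- With positive correlation the 0.05 bound is not breached. The harm is lost power, not false positives.
- The high-correlation rows may be optimistic for comparisons with baseline FSFI, because entry requires a score of 19 or less on the FSFI-6 and so narrows the baseline range. If the screening score correlates 0.9 with baseline FSFI and the lowest 30% to 70% of women are admitted (both assumed), an unselected r of 0.8 falls to 0.65–0.72, and 0.7 falls to 0.53–0.60.
- This is a pilot with no power target, so no promised power is missed.
- Correct calibration raises the expected number of false positives if nothing changes. With 24 unadjusted tests at r = 0.5, it goes from 24 × 0.8% = 0.19 to 24 × 4.79% = 1.15. That is a reason to say how many tests will be read as confirmatory or exploratory, not to keep an unsuitable test.

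**Conclusion.** The concern holds, and the paragraph is wrong as written. It names an independent-samples test and then lists paired comparisons, and no paired method appears anywhere. The mismatch rests on the text alone and needs no assumption.

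Its numerical cost applies only if the rank sum is used within arms, and it depends on the assumed correlation and shift. At r = 0.5 and 0.5 SD, true size is about 0.8% and power about 18% against 42%, so about 30 women would be needed to do the work of 15. At r = 0 there is no cost. If the rank sum is meant only between arms, the fault is instead that 12 to 24 central comparisons have no specified test. Both readings call for the same correction, which should be made before the scores are analysed.

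**What to change.** Replace the test sentence in the statistical paragraph with wording such as:

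> Within each arm, FSFI and SF-36 scores at two time points will be compared with the two-sided Wilcoxon signed-rank test on each woman's change score, reported with the Hodges-Lehmann median change and 95% confidence interval. The Wilcoxon rank sum test will be used only to compare change scores between DGNS and PTNS.

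Also state how zero changes are handled (for example, the Pratt method), which pairs involve the long-term point, and how many women contribute to each comparison. Because the signed-rank test restores the nominal per-test level, say how the set of tests will be interpreted.

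The cost is a few sentences. No extra women or data are needed, since the subject number on each form preserves the pairing. Pairing does not remove bias from selective dropout, and this change is not offered as a remedy for it.

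### Women are randomised to DGNS or PTNS, but the only comparisons spelled out are within each arm over time; the between-arm test has no time point and, read literally, ignores baseline

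*Combined protocol and SAP*

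**What the plan says.** Under Description of methods and analysis: "Patients will be randomly assigned to one of two study groups: receiving DGNS or PTNS". The sample-size paragraph gives 15 women per arm.

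The statistical paragraph of that section makes a non-parametric choice ("Due to the relatively small sample sizes planned for this study, we will use non-parametric statistical testing") and then names a single test at the 0.05 level: "We will use a two-sided Wilcoxon rank sum test to make comparisons of the survey scores among the different subject groups". The next sentence names surveys and time points: "FSFI and SF-36 scores will be compared for each of the potential comparisons among the baseline, 6-week and 12-week study time points". It then adds the late follow-up and restricts all of these comparisons to within-arm use: "at long-term time point, for DGNS and PTNS groups separately".

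The Design overview states the purpose of the surveys as to "evaluate the effects of the experimental stimulation as compared to before study initiation" and to look for a residual effect. Collection, analysis and interpretation of results repeats only a comparison across time points. The sample-size paragraph closes with a consequence: "If one or both stimulation approaches are successful, larger sample sizes will be performed in subsequent studies". Success is not defined. The plan discloses that "we will not have a control stimulation paradigm that does not activate the nerves of interest", and gives feasibility within pilot funding as the reason.

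**The concern.** The two arms were formed by randomisation, so the DGNS-PTNS contrast is the only comparison in this trial that randomisation protects. No section defines it. If the different subject groups are the two arms, the rank sum test has no time point, and scores taken at face value means raw scores. If the test is meant for the time comparisons, no between-arm analysis is planned at all. The gap is there on either reading.

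What is planned in detail is a set of separate before-and-after comparisons in each arm, followed by a possible verdict approach by approach. One significant arm and one non-significant arm do not show that the arms differ. If the two stimulations produce the same rise, chance alone can put one arm below 0.05 and leave the other above it. A later programme could then carry one approach forward and drop the other without evidence for the choice.

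**Working it through.** **Plan's own figure.** There is none to reproduce. The plan says it has no effect size and sets 15 per arm by precedent and feasibility.

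**Inputs.** From the documents: 15 per arm, two-sided 0.05, rank sum test, FSFI at baseline, 6 weeks, 12 weeks and 6 weeks after the end of stimulation. Assumed, because the documents give none: normal scores with SD 1, effects in SD units, and correlation r between baseline and 12-week FSFI.

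**Step 1. What is specified.**
- Within arm: 6 pairs of time points x 2 surveys x 2 arms = 24 comparisons.
- Between arms: no time point chosen from 3 post-baseline ones, and no statement on raw or change scores.

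**Step 2. Equal true rise in both arms: how often is exactly one arm significant?** If each arm is significant with probability p, independently, the chance is 2p(1 - p), with a maximum of 0.50 at p = 0.5. Simulated per-arm power for the rank sum test at r = 0.6 is 0.040, 0.160, 0.469 and 0.798 for rises of 0.3, 0.5, 0.75 and 1.0 SD. The formula gives:
- 2 x 0.040 x 0.960 = 0.077
- 2 x 0.160 x 0.840 = 0.269
- 2 x 0.469 x 0.531 = 0.498
- 2 x 0.798 x 0.202 = 0.322

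Direct simulation gives 0.077, 0.268, 0.503 and 0.323. Across r = 0.6-0.7, by choice of within-arm test:

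| Same rise in both arms | Rank sum | Signed-rank (paired) |
|---|---|---|
| 0.3 SD | 6-8% | 34-40% |
| 0.5 SD | 24-27% | 47-50% |
| 0.75 SD | 49-50% | 14-27% |
| 1.0 SD | 29-32% | 1-5% |

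Both columns peak near one half, at different rises. The peak follows from 2p(1 - p); the choice of test decides where it falls.

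**Step 3. What baseline adjustment gains.** Simulated power for a true 0.75 SD difference between arms:

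| Analysis of 12-week FSFI | r = 0.3 | r = 0.7 |
|---|---|---|
| Rank sum on raw scores | about 47% | about 47% |
| Rank-based, baseline-adjusted (Quade) | 51% | 72% |
| ANCOVA on baseline | 54% | about 78% |

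The two adjusted tests hold their size at about 5% when there is no difference.

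**Step 4. Why not simply test change scores.** With equal SDs, the variance of change is 2(1 - r), against 1 for the raw score. The two are equal at r = 0.5, and change is noisier below that. For a 0.8 SD difference, power on raw scores is about 0.53 at every r. On change it is 0.41, 0.53 and 0.74 at r = 0.3, 0.5 and 0.7.

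**Step 5. Precision of the recommended contrast.** The approximate 95% half-width is t(2n - 3) x sqrt[(2/n)(1 - r^2)], leaving out the small term for chance baseline imbalance. For n = 15, t(27) = 2.052:
- r = 0.6: 2.052 x sqrt(0.1333 x 0.64) = 0.60 SD
- r = 0.7: 2.052 x sqrt(0.1333 x 0.51) = 0.54 SD

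Without adjustment it is t(28) x sqrt(2/15) = 0.75 SD. With 12 evaluable women per arm the adjusted figures are 0.68 and 0.61 SD; with 10 per arm, 0.76 and 0.67 SD.

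**The case against.** This is a disclosed, unpowered pilot whose stated aim is change from before treatment. The text on success only triggers larger later studies, and a statistical consultant is to confirm approaches and conclusions. At 15 per arm a single between-arm test has 80% power only for about (1.960 + 0.842) x sqrt(2/15) = 1.02 SD, so a formal contrast will rarely settle anything. All of this stands, and it makes the point one of specification. It does not remove it: the plan randomises, tests at 0.05 and lets follow-on work depend on success by approach. A wide interval on the right contrast is more honest than two separate p-values. A plain statement that no between-arm inference is intended would be a lesser remedy, but it would leave the randomised information unused.

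It is also fair to say that when both arms truly rise, the significant arm is a correct finding and the other a missed one. The error comes only when the pair is read as one works and the other does not.

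A reader might infer more than the documents support:
- **That the sponsor will rank the arms by separate p-values.** No section says so; the plan leaves it possible.
- **That the plan names no survey.** The sentence after the test names FSFI and SF-36, although for within-arm use.
- **That regression to the mean or concurrent therapy will inflate within-arm gains.** The documents give no interval between screening and baseline, no correlations and no uptake of other treatment. The size cannot be established, and regression to the mean could be zero.
- **That the missing sham is the fault.** It is disclosed with its reason and is not at issue here.

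**Conclusion.** The point holds as a gap that should be closed before analysis. The randomised DGNS-PTNS comparison is not defined: it has no time point, and the literal reading discards the baseline that every woman provides. The planned within-arm tests cannot support a claim that one approach works and the other does not. With equal true effects, such a split can arise in up to about half of trials.

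The upper limit of about one half does not depend on the within-arm test. The rise at which it occurs does, and the tabulated percentages rest on assumed normal scores and r = 0.6-0.7. The power gain from adjustment (about 47% to 51-72% by a rank-based test at 0.75 SD) rests on r = 0.3-0.7, also assumed. The specification gap rests on no assumption. The documents do not show that a wrong ranking of the arms is planned, only that nothing prevents it.

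**What to change.** In the statistical paragraph of Description of methods and analysis:

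1. Name one governing between-arm analysis: the DGNS-PTNS difference in 12-week FSFI adjusted for baseline FSFI, with a 95% confidence interval, in all randomised women as assigned. Report the number without a 12-week FSFI in each arm.
2. To respect the non-parametric choice, take the single between-arm p-value from a rank-based baseline-adjusted test, for example Quade's rank ANCOVA. Do not add a second confirmatory rank sum test on change. It loses power against raw scores if r is below 0.5, and in simulation its verdict differs from ANCOVA in 15-19% of trials at 0.5-0.75 SD (r = 0.6-0.7).
3. Report within-arm changes as uncontrolled and descriptive, and state that the arms will not be ranked from separate within-arm p-values.

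The cost is a few sentences. The FSFI data are already collected, so no extra women or visits are needed. The downsides should be stated in the plan: a half-width of about 0.54-0.60 SD if all 30 women complete and r is 0.6-0.7, wider with dropout or a lower r; relative effect only, because there is no sham; and a weaker claim from within-arm change.

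### FSFI and SF-36 are open to 8 to 32 or more tests with 0.05 the only level given, while the available text fixes no primary comparison and no meaning of success

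*Combined protocol and SAP*

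**What the plan says.** Design overview gives the purpose as evaluating "two skin-surface electrical stimulation approaches for improving sexual arousal". Surveys are used to judge effects "as compared to before study initiation and to look for any long-term residual effect".

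Description of methods and analysis names a two-sided Wilcoxon rank sum test for survey scores between subject groups, "with a significance level of 0.05". The next sentence says that "FSFI and SF-36 scores will be compared for each of the potential comparisons among the baseline, 6-week and 12-week study time points", and extends this to the long-term point, for DGNS and PTNS separately. That sentence names neither a test nor a level.

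The same section makes later work depend on the outcome: "If this study is successful, future proposals to investigate underlying mechanisms may evaluate in vivo effects with animal models". The sample-size paragraph adds: "If one or both stimulation approaches are successful, larger sample sizes will be performed in subsequent studies". Neither place says which result would count.

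Collection, analysis and interpretation of results says that "each survey has a scoring method that yields a total quality of life score and a total sexual satisfaction score" and that these scores are compared over time. It adds that "each survey has sub-sections that we may compare individually, if the data suggests any sub-section trends". It also provides for a statistical consultant to check the approach and conclusions.

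The available text names no primary outcome, primary time point or multiplicity adjustment. The opening part of the document and the appendices were not available.

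**The concern.** Two scales, four time points and two arms allow many tests, and nothing available says in advance which one matters. A team following the text could let the best of many looks, or a sub-section picked because it moved, count as success. A reader could not tell that from a result fixed beforehand. P-values for sub-sections chosen because the data suggested a trend are biased by that choice.

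The aim and the tested scores also do not line up. The purpose is arousal, but the scores fixed for comparison are totals, so an arousal result could enter only by the data-driven route.

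This is a pilot, so what is at stake is the decision to run larger studies, not an efficacy claim.

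**Working it through.** **Inputs.** From the documents: two-sided 0.05, the rank sum test, two scales (FSFI, SF-36), four time points, two arms of 15. The 0.05 is an input, and the sample of 30 has no power basis, so there is no plan figure to reproduce. Assumed, because the documents give no values: within-subject correlation r of 0.3, 0.5, 0.7 or 0.8 (constant over visits or AR(1)), FSFI/SF-36 correlation of 0, 0.3 or 0.6, normal data, no dropout.

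**Step 1: count the tests.**
- Between arms only: 2 scales × 4 time points (baseline included) = 8.
- Within arm, each later visit against baseline: 3 × 2 scales × 2 arms = 12.
- Within arm, all pairs among the first three visits plus long-term against baseline: (3 + 1) × 2 × 2 = 16.
- Within arm, all pairs of four visits: 6 × 2 × 2 = 24.
- All within-arm pairs plus between-arm: 24 + 8 = 32.
- If the between-arm sentence covers all four surveys: 24 + 4 × 4 = 40, or 39 without PGIC at baseline.

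**Step 2: chance of at least one p<0.05 with no true change, rank sum test throughout.** Simulated with exact critical values (size 0.0453 for 15 v 15). Ranges are over the correlation settings.

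| Tests | r = 0.3 | r = 0.5 | r = 0.7 | r = 0.8 |
|---|---|---|---|---|
| 8 between-arm | 27–31% | in between | in between | 19–23% |
| 12 within-arm | 18–30% | 8–20% | 2–9% | 0.3–4% |
| 16 within-arm | 23–34% | 10–22% | 2–10% | 0.4–4% |
| 24 within-arm | 30–43% | 14–28% | 3–12% | 0.6–5% |
| 32 both | 44–55% | 33–44% | 23–32% | 19–26% |

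**Step 3: why the within-arm rows fall.** The rank sum test treats two visits of the same women as independent samples. A difference between visit means has variance proportional to 2(1 − r), but the test behaves as if it were 2. One baseline v 12-week test therefore has actual size 0.020–0.038 at r = 0.3 and 0.0003–0.003 at r = 0.8. Power falls too: for a true mean change of 0.8 SD of change, it is about 54% at r = 0.5 and 28% at r = 0.7, against 80% for the signed-rank test.

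**Step 4: if a paired test were substituted with still no primary.** The chance becomes 35–42% (12 tests), 43–50% (16) or 54–61% (24) over all settings of r.

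**Step 5: one fixed signed-rank test per arm.** Exact size at n = 15 is 0.0479.
- Either direction, over two arms: 1 − (1 − 0.0479)² = 0.0935, about 9.4%.
- Improvements only: 1 − (1 − 0.02395)² = 0.0473, about 4.7%.

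**Step 6: drift without a treatment effect.** There is no control stimulation, and women enter on a low FSFI-6 score, so regression to the mean is possible. For an assumed drift of 0.2, 0.3 or 0.4 SD of change, the chance of a significant improvement in one arm is 0.102, 0.179 or 0.287. In at least one arm:
- 1 − 0.898² = 0.194
- 1 − 0.821² = 0.326
- 1 − 0.713² = 0.492

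**Step 7: power of the single primary.** For a standardised change of 0.6, 0.8 or 1.0, it is 56%, 80% and 94% with 15 completers, and 43%, 67% and 85% with 12.

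**The case against.** A pilot may explore without adjustment, and this one is open about its limits. It says a control paradigm is needed for an ultimate demonstration and will follow once feasibility is shown. It brings in a statistical consultant, and sub-section comparisons are optional. The named test, if used within arms, is conservative: for 12 to 24 tests at r = 0.8 the error is at most about 5%, below the 9.4% of the two-test remedy. That remedy also leads with two uncontrolled before-after tests rather than the only randomised comparison.

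Much of this stands. No family-wide correction is needed. The 9.4% can exceed the unpaired within-arm error at high r; it is the price of a test with close to nominal size and better power. Naming a primary does not cure drift. DGNS v PTNS should stay visible as an estimate.

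The rest does not answer the point. Conservatism that comes from ignoring pairing also hides real change, and it does not apply to the 8 between-arm tests. A consultant who confirms approaches and conclusions fixes nothing in advance unless the text says so. The missing primary and success criterion do not depend on r.

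**Conclusion.** The point holds as a gap in prespecification, of moderate weight for a pilot. The text permits 8 to 32 or more tests, data-driven sub-section tests, and a go-on decision with no stated criterion. Under the named test the false-positive chance is about 19–31% for between-arm tests alone and 19–55% for 32 tests. For within-arm tests alone it runs from 43% down to 0.3%, depending on the count and an assumed r.

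A reader might infer more than the documents support:
- *That 0.05 and the rank sum test are prescribed within arms.* They are attached to comparisons of subject groups. Their use within arms is an inference, drawn because nothing else is given.
- *That the plan carries a 35–61% error.* Those figures belong to a paired test the plan does not name.
- *That the error is 1 − 0.95^m, such as 46% for 12 tests or 81% for 32.* That assumes independence, and these tests are correlated.
- *That any p<0.05 will be declared success.* The text leaves success open; it could mean feasibility.
- *That no primary exists anywhere.* Only the available text can be judged.
- *That dropout is expected.* Potential difficulties says only that compliance may be an issue, and it anticipates willingness similar to other PTNS studies. The 12-completer figures are an assumption.

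**What to change.** - In Description of methods and analysis, name one primary before data are seen. An example is change in FSFI total from baseline to 12 weeks within each arm, by paired signed-rank test at two-sided 0.05. If Appendix 1 confirms an arousal sub-section, the sponsor may choose that instead, because arousal is the stated aim.
- State the overall error over two arms: 9.4% in either direction, 4.7% for improvements only.
- Define success, in both places where it is used, by that primary. Make it a signal to proceed to the controlled study the plan already foresees, not evidence of efficacy, and cite the 19–49% drift figures as the reason.
- Report DGNS v PTNS as the difference in change with a 95% CI.
- Label all other comparisons exploratory, reported as estimates with 95% CIs and without significance claims.
- Replace the data-triggered sub-section rule with reporting of all sub-sections.

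This costs text edits only, with no extra subjects or visits. The price is that secondary results can no longer be called significant and the remaining test has limited power. A non-significant primary would therefore not show absence of effect, and its CI should be reported.
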